We will examine in two short-term placebo-controlled cross-over metabolic studies whether citric acid or potassium citrate can reduce calcium phosphate saturation in urine of CaP stone formers. In the first study (Aims 1 &1a) that was recently conducted in hypocitraturic *CaP stone formers without hypercalciuria*, and we compared the effects of potassium citrate, citric acid and placebo. The results of the study showed that the rise in urinary citrate (an inhibitor of CaP crystallization) with potassium citrate supplementation was negated with a significant elevation in urinary pH resulting in increased urinary supersaturation with CaP salts. *(In this revised version of the protocol we are adding a pilot project as another aim to the first study (Aim 1c), in which* we are proposing a lower dose of potassium citrate sufficient enough to raise the urinary citrate modestly, without altering the urinary pH to negate the protective inhibitory effect of urinary citrate. Aim 1c will recruit up to five patients with calcium phosphate stones CaP regardless of being hypercalciuric or not, and five normal healthy subjects without kidney stones.)

The second study will be conducted in *hypercalciuric CaP stone formers* on a thiazide diuretic who require potassium supplementation, and will compare the effects of potassium chloride alone, potassium chloride + citric acid, and potassium citrate alone. Physicochemical assays will be applied in addition to computer-based stone risk prediction programs to assess risk of stone recurrence.

The proposed small scale clinical pilot studies will use surrogate measures to test two simple interventions. They address a clinical question of utmost importance as we are in dire need of an effective therapy for patients with recurrent CaP stones, a group of stone formers that have not been specifically evaluated in past clinical trials. Results from these studies are likely to lead to full-scale randomized clinical trials with clinical outcomes for the prevention and treatment of recurrent CaP urolithiasis, an increasingly encountered condition in clinical practice.

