Rationale and overall strategy: We will examine whether CitA and/or KCit can reduce the risk of recurrent nephrolithiasis in CaP stone formers. Subjects will be equilibrated on a fixed metabolic diet prior to urine collection for measurement of outcomes. Use of metabolic diet in this pilot study is essential to eliminate potential confounders from differences in dietary intake across phases. Physicochemical assays will be used in addition to computer-based stone risk prediction programs to determine stone risk. Once a regimen is identified, a trial with clinical outcomes can be designed in the future. Inclusion of patients without hypercalciuria will provide a cleaner sample to examine urine pH and citrate. However, since a large portion of CaP formers are hypercalciuric, we need to include these subjects to build a foundation for future trials. Based on the presence or absence of hypercalciuria, CaP stone formers will be included into 2 separate Aims.

Study Protocol:

Study Design & Methods:

Aim 1: Calcium phosphate stone formers without hypercalciuria

Subjects: 25 hypocitraturic stone formers without hypercalciuria will participate in this 3-phase cross-over metabolic study. Subjects will be recruited from the UTSW Mineral Metabolism and Urology clinics.

Inclusion criteria: Hypocitraturic CaP stone formers with elevated urine pH will be >21 years, of either gender, any race and ethnicity. Hypocitraturia will be defined as 24-hr urine citrate < 320 mg/d and elevated pH as 24-hr urine pH above 6.40^{6,7} in the absence of urinary tract infection. CaP stone disease will be defined based on most recent available stone composition with CaP constituting over 70% of overall stone components.

Exclusion criteria: History of recurrent urinary tract infections, conditions that predispose to acid-base disorders such as chronic diarrhea, estimated GFR<60 ml/min, chronic use of non-steroidal anti-inflammatory drugs, angiotensin 2 receptor blockers, ACE-inhibitors, diuretics, antacids or alkali treatment, and carbonic anhydrase inhibitors. Patients with hypercalciuria (24-hr urine calcium > 250 mg/day) will be allocated to Aim 2.

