Study protocol: In this double-blind, placebocontrolled, crossover study, each subject will undergo 3 phases, the order of which will be randomized by a simple randomization scheme. The 3 phases will be Placebo (PBO), Citric Acid (CitA), and Potassium Citrate (KCit). Each phase will be 1 week in duration, during which subjects will take assigned study medications. A 1-week washout period is imposed between phases (Figure 1). During the first 2 days of each phase, subjects will be instructed to adhere to a diet at home with a daily composition of 800 mg calcium, 100 mEq sodium, 800 mg phosphorus, 50 mEq potassium

and 2 liters of total fluids daily. On the last 5 days of each phase, subjects will be kept on a constant metabolic diet of the same composition provided by the Clinical Research Unit (CRU). During the final two study days (days 6-7), subjects will be admitted to the CRU where a 22-hr urine and 2-hr fasting urine will be collected on day 6 under mineral oil to measure urine chemistries (stone risk factors) and acid-base parameters, and on day 7 for crystallization studies. Fasting blood will be obtained at the end of each urine collection.

Study Medications: Subjects will receive three 10 mEq tablets of CitA twice a day during the CitA phase (60 mEq/day), two 10 mEq KCit tablets and one placebo tablet twice a day during the KCit phase (40 mEq/day), and 3 tablets twice daily of matching placebo during the PBO phase. Study tablets are prepared by a compounding pharmacy, with placebo tablets similar in appearance and size to the active medication tablets.

Sample size: This was calculated based on our preliminary studies. 20 subjects will provide a power of 0.80 at the 0.015 level of significance (to adjust for multiple comparisons of the three phases) to detect a difference of 0.3 units in CPR brushite, between treatment and placebo phases (within subject standard deviation of 0.38). Assuming 20% withdrawal, 25 subjects will be enrolled with the expectation that 20 subjects will complete the entire study.

Serum: Blood will be collected for measurement of serum sodium, potassium, chloride, CO₂, glucose, BUN, creatinine, calcium, albumin, magnesium, phosphorus, and uric acid. These will be measured primarily to assure subject safety (e.g. hyperkalemia, renal insufficiency, metabolic acidosis/alkalosis).

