24-hr urine stone risk factors: These are well established at the UT Southwestern Mineral Metabolism Laboratories:⁸ urine pH, citrate, calcium, phosphorus, oxalate, uric acid, ammonium, sulfate, chloride, sodium, potassium, magnesium, total volume, creatinine, TA, HCO₃⁻. These parameters will be combined to calculate saturation by JESS and compared individually across phases.

Saturation: Urine saturation will be directly measured by CPR as previously described⁹, and will be calculated from the measured urinary parameters by JESS as Saturation Index^{1, 2, 10}.

Additional physicochemical measures: In addition to CPR, we will assess *crystal growth (CG)* of brushite after seeding urine with a small amount of brushite (0.25 mg/ml urine) as previously described¹¹. We will also measure overall activity of urinary promoters and inhibitors to brushite crystallization as *formation product (FP)*. This will be based on an established method to assess the limit of metastability of brushite¹². FP is obtained by adding increasing amount of Ca to a series of aliquots of urine at constant pH for 2hrs, and is identified by the point at which visible brushite precipitation is elicited. Calculated SI using [Ca] and [P] at that point represents FP brushite. Measurement of CG and FP brushite will provide additional insights on the effects of KCit and CitA on CaP stone formation beside their effect on saturation, since the process of kidney stone formation depends on the complex interplay between these three factors.

Statistical Analysis: For each phase, descriptive statistics will be computed for continuous variables. Data transformation or nonparametric tests will be utilized as

needed to meet analysis assumptions. For this crossover design, repeated measures analysis will be implemented to assess treatment effects for biochemical parameters¹³. A Bonferroni-Hochberg adjustment will be used to adjust for multiple testing¹⁴. A mixed model approach will be used so that the covariance structure can be specified. If necessary,

	Urine			Brushite		
	Cit	pН	Ca	CPR / SI	CG	FP
CitA	↑	\leftrightarrow	\leftrightarrow	\rightarrow	\rightarrow	↑
KCit	↑	1	\downarrow	$\leftrightarrow/\downarrow$	↓	↑

Expected changes (↔, ↑, or ↓) compared with placebo IRB # 032012-058 pairwise multiple comparisons will be made with with contrasts derived from the repeated measures models.

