Study protocol: In this double-blind. placebocontrolled crossover study. each hypercalciuric CaP stone former will undergo 3 phases, the order of which will be randomized by а simple randomization scheme.

Phase	Ind+KCI+PBO	Ind+KCI+CitA	Ind+KCit+PBO	
Potassium dose	20 mEq BID KCI	20 mEq BID KCI		
Citrate dose	None	20 mEq BID CitA		
Expected effect on urine pH	\leftrightarrow	\leftrightarrow	1	
Expected effect on urine citrate	\leftrightarrow	1	\uparrow	
Expected effect on urine calcium	\leftrightarrow	\leftrightarrow	\downarrow	
Expected effect on CPR(brushite)	\leftrightarrow	\rightarrow	\downarrow	

Table 2. Experimental design and expected findings in Aim 2. Ind: Indapamide; PBO: Placebo. Note that "Expected effects" in this table represent the expected effects of KCl vs. KCl+CitA vs KCit beyond effect of indapamide which will be fixed throughout the study

Study medications: The 3 phases will be Indapamide+KCI+PBO, Indapamide+KCI+CitA, and Indapamide+KCit+PBO. The dose of indapamide will be fixed at 1.25 mg/day in each subject, the amount of potassium provided as KCit or KCI will be kept constant at 20 mEq BID, and the amount of Citrate provided either

as KCit or CitA will be 20 mEq BID (Table 2). This will allow for direct assessment of effects of KCl vs. KCl+CitA vs. KCit. Subjects will be studied in the same experimental protocol described in Figure 1.

Inclusion criteria: Hypercalciuric CaP stone formers with elevated urine pH will be >21 years, of either gender, any race and ethnicity. Hypercalciuria will be defined as 24-hr urine calc ium > 250 mg/d in women and > 300 mg/d in men prior to indapamide use, and high pH as >6.40 in the absence of urinary tract infection. CaP stone disease will be defined based on most recent available stone composition with CaP constituting over 70% of overall stone components. Subjects will be included irrespective of urinary citrate

Exclusion criteria: Same as in Aim 1 except for hypercalciuria.

Analyses: Analyses will be conducted in a similar fashion to those described under Aim 1.

Aim 2a Optional Outpatient Study:

Subjects: Patients being enrolled into Aim 2 will be given the option to participate in the study as an outpatient if it is more convenient.

Inclusion criteria: Same as above.

Exclusion criteria: Same as above.

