Study protocol: In this double-blind, placebo-controlled crossover study, each hypercalciuric CaP stone former will undergo 3 phases, the order of which will be randomized by a simple randomization scheme. The 3 phases will be Indapamide+KCI+PBO, Indapamide+KCI+CitA, and Indapamide+KCit+PBO. The dose of indapamide will be fixed at 1.25 mg/day in each subject, the amount of potassium provided as KCit or KCI will be kept constant at 20 mEq BID, and the amount of Citrate provided either as KCit or CitA will be 20 mEq BID (Table 2). This will allow for direct assessment of effects of KCI vs. KCI+CitA vs. KCit. During the first 4 days of each phase, subjects will be instructed to adhere to a diet at home with a daily composition of 800 mg calcium, 100 mEq sodium, 800 mg phosphorus, 50 mEq potassium and 2 liters of total fluids daily. On the last 3 days of each phase, subjects will be kept on a constant metabolic diet of the same composition provided by the Clinical Research Unit (CRU). During the final two study days (days 6-7), subjects will collect a 24 hour urine at home on day 6 for crystallization studies, and also under mineral oil on day 7 to measure urine chemistries (stone risk factors) and acid-base parameters. The subjects will bring the urine to the Mineral Metabolism Clinic at Aston on the morning of day 8. Fasting blood will be obtained in the Mineral Metabolism Clinic on day 8 during this visit.

Protection of Human Subjects

1. 1. Risks to the Subjects

Human Subjects Involvement and Characteristics

Aim 1

3-phase, double-blind, cross-over metabolic study examining the effects of potassium citrate and citric acid on urinary predictors of stone formation in calcium phosphate stone formers *without* hypercalciuria

Disease State	Subject Number	Inclusion Criteria	Exclusion Criteria
Calcium phosphate stone formers without hypercalciuria	25	 ≥ 21 years of age for all subjects Stone analysis showing calcium phosphate as major component of stone (>70%) Hypocitraturia (urine citrate < 320 mg/d) 24hr urine pH>6.40 	 Hypercalciuria (24h urine calcium > 250 mg/day) Recurrent urinary tract infections Chronic diarrhea Endogenous creatinine clearance < 70ml/minute by eGFR Chronic use of non-steroidal anti-inflammatory drugs, angiotensin 2 receptor blockers, ACE inhibitors, diuretics, antacids/alkali treatment, or carbonic anhydrase inhibitors

Aim 2

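### Aims 2/2a: the analysis text does not say whether period is in the model, and phase order is set by simple randomization; stating a period term, and blocking the orders if still possible, is a minor gain in precision

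*Combined protocol and SAP*

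**What the plan says.** The Study protocol paragraphs of Aims 2 and 2a describe three phases per subject, "the order of which will be randomized by a simple randomization scheme". Neither names blocks, a Latin square or a list of sequences. Aim 2a is the outpatient option of Aim 2: "Patients being enrolled into Aim 2 will be given the option to participate in the study as an outpatient if it is more convenient".

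For the analysis, Aim 2 says only: "Analyses will be conducted in a similar fashion to those described under Aim 1". The Aim 1 Statistical Analysis text reads: "For this crossover design, repeated measures analysis will be implemented to assess treatment effects for biochemical parameters". It adds a mixed model with a specified covariance structure, a multiplicity adjustment and pairwise contrasts, and it cites a textbook on cross-over trials. It does not list the fixed effects, so a period term is neither stated nor excluded.

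The subject table gives 25 for Aim 2. The only sample size calculation is Aim 1's, with a "within subject standard deviation of 0.38" and this allowance: "Assuming 20% withdrawal, 25 subjects will be enrolled with the expectation that 20 subjects will complete the entire study". The objectives put Aim 2 in the future tense ("The second study will be conducted in" hypercalciuric stone formers), but enrolment status is not given.

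**The concern.** Three treatments in three periods allow six orders (inferred; the documents do not list them). With about 20 completers, simple randomization spreads the treatments unevenly over periods 1 to 3 by chance. If urine saturation drifts from one phase to the next and the model has no period term, the drift adds noise to every treatment comparison. If the model does have a period term, the uneven spread still costs a little precision. What is at stake is some power in a small study, and a modelling choice that would otherwise be made after the data are in hand.

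**Working it through.** **Inputs.** From Aim 1, Sample size: 20 completers, difference 0.3 in CPR brushite, alpha 0.015, SD 0.38, 20% withdrawal (25 × 0.80 = 20). Aim 2 has no calculation of its own, so applying these to it is an assumption. Sidedness is not stated; two-sided is assumed. Drift per period is not given; linear drifts of 0 to 0.15 CPR units per period are assumed.

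**The plan's own figure.** A paired t-test with SD of the difference 0.38 has noncentrality 0.3 / (0.38/√20) = 0.3/0.0850 = 3.53. With 19 df the power is 0.794, against the stated 0.80. If 0.38 is the within-subject SD, as it is labelled, the SD of the difference is 0.38 × √2 = 0.537, the noncentrality is 2.50 and the power is 0.449. The first reading reproduces the plan; both are carried below.

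**No period term, simple randomization.** The positions of two treatments differ by ±1 in four of the six orders and by ±2 in two, so the mean squared difference is (4×1 + 2×4)/6 = 2. Averaged over 20 subjects, the SD of the difference in mean position is √(2/20) = 0.32 periods. A drift d per period therefore adds 2d² to the variance of a subject's paired difference, that is, d² to the within-subject variance. At d = 0.15 the within-subject variance rises from 0.38²/2 = 0.0722 to 0.0722 + 0.0225 = 0.0947. The standard error grows by √(0.0947/0.0722) = 1.145 and the noncentrality falls to 3.53/1.145 = 3.08. Power drops from 0.831 (38 df, no drift) to about 0.70, and simulation agrees. The added noise also enters the residual, so the test stays honest: simulated type I error is 0.0149 to 0.0154 for drifts of 0 to 0.15.

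**Period term in the model.** Period effects are removed, so power does not depend on drift. The price is 2 df (38 to 36) and variance inflation from uneven orders:

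- Simple randomization, 20 subjects: mean inflation 1.057, 95th percentile 1.18, mean SE factor 1.028.
- Blocks of six, 25 assigned and 5 lost at random: mean inflation 1.012, 95th percentile 1.03, mean SE factor 1.006.

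The ratio 1.006/1.028 = 0.979, so blocking makes the standard error about 2% smaller.

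**Power, two-sided alpha 0.015** (first figure: 0.38 as SD of the difference; second: 0.38 as within-subject SD)

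| Drift per period | Simple, no period term | Simple + period term | Blocks + period term |
|---|---|---|---|
| 0 | 0.831 / 0.487 | 0.805 / 0.460 | 0.824 / 0.479 |
| 0.05 | 0.817 / 0.479 | 0.805 / 0.460 | 0.824 / 0.479 |
| 0.10 | 0.773 / 0.455 | 0.805 / 0.460 | 0.824 / 0.479 |
| 0.15 | 0.700 / 0.420 | 0.805 / 0.460 | 0.824 / 0.479 |

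Against simple randomization with no period term, both changes together break even at a drift of about 0.035 (or 0.05 on the second reading). The period term alone breaks even between 0.05 and 0.10 on either reading.

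**Blocks without a period term.** At drift 0.15, power is 0.716 against 0.699 under simple randomization, and type I error falls to 0.008. Blocking is therefore no substitute for the term.

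**The case against.** The strongest reply is that nothing here is wrong. Simple randomization of orders is valid, the study calls itself a small pilot, and the analysis text speaks of a crossover design, specifies a mixed model and cites a cross-over textbook, so a period term may well be intended. If it is, only the two-point gain from blocking remains. The sign of the benefit against a model without the term depends on a drift that the documents do not give. Diet is controlled for this very reason: "Use of metabolic diet in this pilot study is essential to eliminate potential confounders from differences in dietary intake across phases". A drift of 0.15 per period amounts to 0.30 over the study, as large as the target difference. Blocks also make late allocations somewhat predictable to anyone who knows the block size.

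Most of that stands, and it is why the point is minor. What it does not answer is that the fixed effects are left open, and one sentence closes the matter. The diet argument makes large drift less likely without showing that it is absent. The washout bears on carryover rather than drift. Double-blinding and a concealed list limit the predictability.

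A reader might infer that simple randomization biases the comparison or inflates false positives. It does not: type I error stays at about 0.015. A reader might also infer that the plan omits a period term; the text is silent, which is not the same. Finally, the chance that one of the six orders goes unused (15.2% of draws under simple randomization, 0.2% under blocks) may look alarming. It has no consequence here beyond the variance inflation already counted.

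**Conclusion.** The point holds as a low-priority improvement in precision. The period term does most of the work: under simple randomization it holds power at about 0.80 whatever the drift, where leaving it out gives 0.83 with no drift and about 0.70 at 0.15 per period. Blocking adds about 0.02 (0.805 to 0.824, or 0.460 to 0.479 on the other reading of the SD). For drift up to about 0.05 per period there is no clear gain even from both changes.

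This rests on Aim 1's difference, SD and withdrawal rate applying to Aim 2, on a two-sided test, on assumed linear drifts, and on simple meaning unrestricted. The two readings of 0.38 move power far more than this point does, and are a separate matter.

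**What to change.** **First, whether or not orders are already assigned.** Add to the Aim 2 analysis text, before unblinding, and make clear that it covers Aim 2a: *The mixed model will include treatment and period as fixed effects and subject as a random effect.* Cost: one sentence and 2 of 38 error df. With no drift under simple randomization, power falls by about 0.03 (0.831 to 0.805; 0.487 to 0.460 on the other SD reading).

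**Second, only if orders are not yet assigned.** Replace simple randomization in Aims 2 and 2a with a concealed, computer-generated list of permuted blocks, each block holding the six orders once. One list for both settings or one list per setting works about equally well (inflation 1.012 to 1.016). Make this change only together with the first. Cost: one allocation list, and some predictability late in a block. With both changes the loss at zero drift shrinks to about 0.007 (0.831 to 0.824). If orders are already assigned, keep the allocation.

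**Other aims.** Aim 1b uses the same allocation wording and is not among the aims described as already conducted; the same change would apply there if its orders are still open. Leave the allocation of Aims 1 and 1a as it is. No figure here is meant for Aim 1c.

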Exclusion criteria: History of recurrent urinary tract infections, chronic diarrhea, estimated eGFR <60 ml/min and chronic use of non-steroidal anti-inflammatory drugs, angiotensin 2 receptor blocker, ACE-inhibitors, diuretics, antacids, alkali treatment and carbonic anhydrase inhibitors.

Study protocol: In this double-blind, placebo-controlled, crossover study, each subject will undergo 3 phases, the order of which will be randomized by a simple randomization scheme. In this aim, we will utilize the following medications during the 3 phases:

- a. Control, no medication
- b. Potassium Citrate 5mEq 1 pill, 2 times a day
- c. Potassium Citrate 10mEq, 1 pill, 2 times a day

In each phase, the subjects will be instructed to adhere to a diet on a instructed diet consisting of 800 mg calcium, 800 mg phosphorus, 100 mEq of sodium, 50 mEq of potassium and 2 liters of fluids daily at home. On the third day of the study, while on the instructed diet the subjects will collect 24-hour urine at home for the kidney stone risk profiles. The subjects will bring the urine to the Mineral Metabolism Clinic at Aston, 9th floor on the morning of day 4.

The rationale for the adjustment in medication dose/frequency of the Potassium Citrate is evidenced in the recently completed three phases of the study control, potassium citrate and citric acid in calcium phosphate stone formers. The results of the study showed that the rise in urinary citrate (an inhibitor of CaP crystallization) with potassium citrate supplementation was negated with a significant elevation in urinary pH resulting in increased urinary supersaturation with CaP salts. In this aim, we are proposing a lower dose of potassium citrate sufficient enough to raise the urinary citrate modestly, while does not alter the urinary pH to negate the protective inhibitory effect of urinary citrate.

Aim 2: Calcium phosphate stone formers with hypercalciuria

Rationale: Since the majority of CaP stone formers are hypercalciuric (60-80%), we will separately study this group with a similar 3-phase design. In our practice, these patients are all prescribed a thiazide diuretic (generally indapamide due to its long half-life, allowing once a day dosing) to reduce hypercalciuria along with a potassium supplement to avert thiazide-induced hypokalemia¹⁹. However, it is unclear whether KCl or KCit is the optimal K supplement for CaP stone formers on a thiazide diuretic.

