3-phase, double-blind, cross-over metabolic study examining the effects of potassium citrate and citric acid on urinary predictors of stone formation in calcium phosphate stone formers *with* hypercalciuria

Disease State	Subject Number	Inclusion Criteria	Exclusion Criteria
Calcium phosphate stone formers with hypercalciuria	25	 ≥ 21 years of age for all subjects Stone analysis showing calcium phosphate as major component of stone (>70%) Hypercalciuria (urine calcium > 250 mg/d in women and >300 mg/d in men) 24hr urine pH>6.40 	 Recurrent urinary tract infections Chronic diarrhea Endogenous creatinine clearance < 70ml/minute by eGFR Chronic use of non-steroidal anti-inflammatory drugs, angiotensin 2 receptor blockers, ACE inhibitors, diuretics, antacids/alkali treatment, or carbonic anhydrase inhibitors

Prisoners, institutionalized individuals, children under the age of 21 and pregnant women will be excluded from all studies.

Sources of Materials: Results from medical, diet history, pregnancy tests, blood and urine tests, physical examinations, medication and dietary compliance, and demographics will be used in this study and accessed by the study investigators, research coordinator and study nurses and the biostatistician.

Research data recorded in this study will include:

- Medical History: medications, surgeries, allergies, use of alcohol and/or tobacco,
- Pregnancy test results
- Blood tests: Comprehensive metabolic panel (sodium, potassium, chloride, bicarbonate, glucose, BUN, creatinine, calcium, total protein, albumin, bilirubin, alkaline phosphatase, AST, ALT), magnesium, phosphorus and uric acid.
- Urine tests: total volume, pH, creatinine, sodium, potassium, calcium, magnesium, phosphorus, oxalate, uric acid, sulfate, citrate, chloride and ammonium, spot urinalysis, pregnancy test, and physicochemical assays (concentration product ratio, crystal growth, formation product).
- Physical examinations: diet history, height and weight, blood pressure
- Assessments from clinic visits: adverse events, medication and dietary compliance
- Demographics: name, date of birth, gender, and race/ethnic background

Potential Risks: Risks are enumerated in the consent form associated with the study that is explained to and signed by the participants. Individual aims may include some or all of the risks listed below:

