- *Blood Draws* Some common risks from venipuncture include discomfort, bleeding and/or bruising, dizziness or feeling faint. On a rare occasion, an infection could develop at the site where blood was collected.
- *Potassium Citrate* may cause diarrhea, nausea and abdominal cramping and a high blood potassium level. Signs of high potassium levels include feeling weak, lightheaded, dizzy, or having numbness or tingling.
- *Citric Acid* is a weak organic acid found in a variety of citrus fruits and vegetables; it is commonly used as a natural preservative or to improve taste to foods and soft drinks.

Subjects will be advised beforehand of the nature of potential side effects. Those with an increased risk of injury or side effects will be excluded from the study. If adverse symptoms appear, patients will be asked to contact the investigators.

2. Adequacy of Protection Against Risks

Recruitment and Informed Consent: Recruitment of subjects will be attempted via referral from the UT Southwestern Medical Center Urology and Mineral Metabolism Clinics. Consent of patients will be obtained prior to their involvement in the study by one of the investigators and will be witnessed by personnel not involved in the study. The subjects will receive a copy of the IRB-approved consent and a copy will be maintained in their research chart. All efforts will be utilized to ensure subject privacy and all data will be held confidentially. HIPPA regulations will be discussed with all participants and HIPPA consent will be obtained concurrently with the study consent.

Protection Against Risk: Subjects will be screened for any diseases that would increase the likelihood of side effects. Subjects will be closely monitored for any adverse effects and investigators will be alerted immediately in the case of any untoward outcomes. Participation in the study will be terminated if the subjects encounter any serious adverse effects.

3. Potential Benefits of the Proposed Research to the Subjects and Others

The immediate benefits to participants of the study will be limited. Subjects will receive the results of their laboratory work and will receive financial reimbursement for their time. The risks are minimal and are acceptable when the potential benefits are considered. The benefits mainly include the knowledge that may be gained regarding risk of recurrent urinary stones, which in the long-term could impact the care of the subjects themselves.

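### The Aim 2 exclusions bar chronic diuretic use without exempting a thiazide or indapamide, so read literally they shut out established members of the population that Aim 2 names

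*Combined protocol and SAP*

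**What the plan says.** **Population.** Under Specific Aims, the second study is set in hypercalciuric calcium phosphate stone formers "on a thiazide diuretic who require potassium supplementation". The Aim 2 Rationale puts the research question for the same group: whether KCl or KCit "is the optimal K supplement for CaP stone formers on a thiazide diuretic". It describes local care in these words: "In our practice, these patients are all prescribed a thiazide diuretic", with indapamide the usual choice, "along with a potassium supplement to avert thiazide-induced hypokalemia".

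**Exclusions, Aim 2 text.** "Exclusion criteria: Same as in Aim 1 except for hypercalciuria". The Aim 1 list that this brings in covers chronic use of several drug classes, among them "diuretics, antacids or alkali treatment, and carbonic anhydrase inhibitors". Aim 2a takes over the same criteria.

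**Exclusions, Aim 2 table** (Human Subjects Involvement and Characteristics). "Chronic use of non-steroidal anti-inflammatory drugs, angiotensin 2 receptor blockers, ACE inhibitors, diuretics, antacids/alkali treatment, or carbonic anhydrase inhibitors". This line is identical to the one in the Aim 1 table.

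**Indapamide.** Aim 2, Study medications, gives indapamide in all three phases at 1.25 mg/day. The Aim 2 inclusion text judges hypercalciuria on urine calcium before indapamide; the Aim 2 table gives the same calcium limits without that qualifier. The note to Table 2 treats the indapamide effect as constant for the whole study.

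**Source of subjects** (Recruitment and Informed Consent). "Recruitment of subjects will be attempted via referral from the UT Southwestern Medical Center Urology and Mineral Metabolism Clinics".

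**The concern.** The two exclusion statements agree with each other but not with the stated population. The Aim 1 list appears to have been adapted for Aim 2 in one respect only, the removal of hypercalciuria. A diuretic exclusion makes sense in Aim 1, where no subject should be on a thiazide. In Aim 2 the thiazide is the background treatment against which the potassium supplements are compared.

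Two things are at stake. The first is recruitment: established patients of the two referring clinics are a natural source for the 25 planned subjects, and the rule closes it. The second is the population to which the result applies. If only untreated patients enter, the trial informs the choice of supplement in people newly started on indapamide, a narrower group than Specific Aims and the Aim 2 Rationale describe. A rule at odds with the stated population also invites inconsistent screening decisions.

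**Working it through.** The plan gives no figure on this point to reproduce. The check is a comparison of texts, followed by a small count of days.

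**1. Apply the rule to the possible candidates.**

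| Candidate at screening | In the population named in Specific Aims? | Admitted by the Aim 2 exclusions as written? |
|---|---|---|
| Established on a thiazide or indapamide | Yes | No: chronic diuretic use, no exemption |
| Untreated new referral, to start study indapamide | Only once indapamide has begun | Yes |
| Established user whose thiazide is stopped before screening | Yes, before stopping | Unclear: no thiazide washout is described |

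The one group that clearly fits the stated population at screening is the one that the rule clearly rejects.

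**2. Does the pre-indapamide calcium qualifier settle which group is meant?** No. A calcium value from before indapamide can be a historical value in an established patient or a screening value in an untreated one. The Aim 2 table omits the qualifier, which fits patients screened untreated but does not require it.

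**3. What follows if indapamide is started in the study?** Inputs from the Aim 1 study protocol, which Aim 2 adopts by reference to Figure 1: phases of 7 days, washouts of 7 days, outcome urines on days 6 and 7 of each phase. Aim 2a uses the same outcome days.

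- Days elapsed before phase k: (k − 1) × (7 + 7) = 0, 14, 28.
- Started on day 1 of phase 1 and continued, indapamide has been taken at the outcome urines for 0 + 6 to 0 + 7 = 6–7 days, 14 + 6 to 14 + 7 = 20–21 days, and 28 + 6 to 28 + 7 = 34–35 days.
- Given only within phases, it has been taken for 6–7 days each time, in phases 2 and 3 after 7 days off.
- Schedule length: 28 + 7 = 35 days, or 5 weeks.

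The text does not say when indapamide starts or whether it continues through the washouts. Nor does it say how soon the effect settles, so these counts show that a constant effect is not secured, not that it fails. Because phase order is randomized, unequal exposure would act as a period effect, not as a systematic difference between treatments.

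**4. Size of the recruitment loss.** It equals the share of otherwise eligible candidates already on a thiazide at screening. The plan does not give that share or any bounds for it, so no figure can be put on the loss.

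**The case against.** The strongest reply is that the exclusion screens medication taken before the trial, while indapamide is trial medication. It is listed as such, at one fixed dose in every phase, so every Aim 2 subject would be on a thiazide during the comparison, as Specific Aims says. The statement about local practice describes a prescribing policy. It does not say that candidates are already treated when screened, and a newly diagnosed patient about to be prescribed a thiazide fits it equally well. Excluding established users is also defensible, since it avoids mixed prior exposure.

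Much of this stands. It rules out a stronger conclusion that a reader might infer, that Aim 2 forbids its own background drug or can enroll nobody. Untreated referrals remain eligible, and nothing in the plan shows that they are few.

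What the reply does not do is supply the missing statement. The plan nowhere says that subjects must be untreated or washed out at entry, and Specific Aims and the Rationale describe the target group simply as being on a thiazide.

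On timing, the Table 2 note is most naturally read as indapamide continuing across phases and washouts. Figure 1 was not visible in the text examined. If it shows the indapamide schedule, the timing remark falls, but the conflict over eligibility remains.

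**Conclusion.** The point holds as a conflict between the stated Aim 2 population and both operative exclusion statements. Read literally, they exclude established members of the population that the aim names and leave only patients not yet on a diuretic. That may be what the sponsor intends, but the plan does not say so.

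The harm is to recruitment and to the reach of the result, and its size cannot be determined. A reader might go further and infer a biased comparison of KCl, KCl plus citric acid and KCit. The documents do not support that: each subject serves as his or her own control, the indapamide dose is the same in every phase, and phase order is randomized. Nor do they show that the three regimens compare differently in new and established thiazide users, so the loss of generalizability is a possibility, not a demonstrated effect.

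The conclusion rests on reading chronic diuretic use in its ordinary sense, which includes a long-term thiazide. The wording should be settled before Aim 2 screening.

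**What to change.** **Main change.**

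- In the Aim 2 exclusions, both in the text and in the table, replace the bar on diuretics with *diuretics other than a thiazide or indapamide*.
- In the Aim 2 table, add that hypercalciuria is judged on urine calcium *before any thiazide or indapamide*. Extend the existing indapamide qualifier in the Aim 2 inclusion text to thiazides.
- State that every subject takes indapamide 1.25 mg/day from before phase 1 and continues it through the washouts, with potassium cover as KCl. The effect is then held constant as the Table 2 note intends, hypokalemia is guarded against as in the Rationale, and the washout applies to KCit and citric acid.

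The length of any lead-in is for the sponsor to choose, as the plan gives none. As an illustration only, an assumed 1 or 2 weeks would put the first outcome urine at day 7 + 6 = 13 or 14 + 6 = 20 of indapamide, and lengthen the schedule from 5 weeks to 5 + 1 = 6 or 5 + 2 = 7.

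The sponsor would also need to say how users of another thiazide move to indapamide, when urine pH is judged, and what happens to established patients whose potassium supplement is KCit, since the alkali exclusion would still bar them.

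**Cost.** Short wording changes in the eligibility sections and a few sentences on timing; possibly a short lead-in, with the added indapamide and KCl exposure; and some variation between subjects in prior thiazide exposure. No added subjects.

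**Alternative.** If only patients not on a diuretic at entry are intended, say so under Specific Aims and limit the conclusion to patients newly started on indapamide. This costs a sentence or two and leaves the exclusions as they are. The timing of indapamide should still be stated.
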